### 8.2.2.2 Derivation of seizure frequency related variables

The following variables will be defined for each visit and Month 12 /Withdrawal using the 28-day Baseline and 28-day post-Baseline seizure frequency variables described in [Section 8.2.2.1](#).

- Absolute reduction in POS frequency defined as:  
$$28\text{-day Baseline} - 28\text{-day post-Baseline seizure frequency}$$
- Percent reduction in POS frequency defined as:  
$$\frac{28\text{-day Baseline} - 28\text{-day post-Baseline seizure frequency}}{28\text{-day Baseline}} \times 100$$
- Patients with 0 POS at Baseline will be excluded from the analysis of percent reduction and response ( $\geq 50\%$ ).
- Response (Yes, No) where Yes is  $\geq 50\%$  reduction in POS frequency calculated as described above and No otherwise.
- Seizure freedom (Yes, No) will be defined using 2 methods as shown in [Table 8-1](#). The first method considers patients who withdraw prior to their 1st seizure as Not seizure free. The 2nd is a less conservative method which considers patients who withdraw prior to their 1st seizure as missing. Visit 4 (Month 12/Withdrawal) will not be summarized for seizure freedom.

Table 8–1: Derivation of seizure freedom		
Patient Classification at Visit (patients are assigned to the first category they fall into)	Seizure freedom – Discontinuations counted as not seizure free	Seizure freedom – Discontinuations counted as missing
0. Patients had a seizure before 1st BRV dose	Missing	Missing
1. Patient had a seizure on or after 1st BRV dose and on or before the visit date derived using the following conditions. First_seizure_date = Date of first seizure or if date of first seizure is missing but patient has seizures recorded at a visit, then assign first_seizure_date as the date of the visit prior to the earliest visit with seizures recorded a) Visit date present and First_seizure_date is on or after 1st BRV and on or before the Visit date b) Visit date is missing (either due to patient ongoing in study or visit missed) and First_seizure_date is on or after 1st BRV and on or before the visits target day [a])	No	No
2. Patient discontinued BRV or terminated the study prior to the visit’s target day [a]	No	Missing

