3. Patient had missing seizure data at the visit (or missed the visit) but had not discontinued BRV or terminated the study prior to the visit’s target day [a]. Note: If a patient is ongoing in the study and had not got to the visit yet, they are treated in the same way as having missed visit.	Missing	Missing
4. Patient met none of the above classifications and patient has the visit present	Yes	Yes

[a] The target day for each visit is: Visit 2 (Month 3) = Day 90, Visit 3 (Month 6) = Day 180, and Visit 4 (Month 12) = Day 330. For Month 12 assessments, seizure freedom will be analyzed for completers only. Therefore assign missing to all patients who withdraw for the Month 12 analyses.

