### 8.2.3 Time to first seizure

The time to the first seizure (days) will be calculated as:

Date of first seizure in the trial – date of first BRV administration + 1

If the exact date of first seizure cannot be determined but the patient has had seizures recorded post Visit 1, then the patient will still be counted as having an event using a conservative approach as shown in [Table 8–2](#).

For patients with no evidence of seizures, the following sequential approach will be taken which is further detailed in [Table 8–2](#):

1. For patients attending a visit but with missing seizure data, they will be censored at the date of the last visit prior to the visit with the missing seizure information.
2. For patients discontinuing BRV study medication before experiencing their first seizure, they will be censored at the date of last administration of BRV while in the study.
3. For patients with no recorded seizures and still on BRV study medication, they will be censored at the date of last visit.

As the approach used is very conservative, if there are a lot of patients censored in the early visits due to missing data or with early events due to missing data, a sensitivity analysis may be performed.

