**Table 8–2: Derivation of time to first seizure**

Missing date of first seizure but seizures recorded				No evidence of seizures on the study			
V2	V3	V4	Date used	V2	V3	V4	Date used
M	M	>0	E-V1/1BRV [a]	M	M	M	C-V1
M	>0	NA	E-V1/1BRV [a]	0	M	M	C-V2
>0	NA	NA	E-V1/1BRV	M	0	M	C-V1
0	>0	NA	E-V2	M	M	0	C-V1
0	0	>0	E-V3	0	0	M	C-V3
M	-	>0	E-V1/1BRV [a]	0	M	0	C-V2
0	-	>0	E-V2	M	0	0	C-V1
-	>0	NA	E-V1/1BRV [a]	0	0	0	C-V4
-	M	>0	E-V1/1BRV [a]	0	Disc BRV	NA	C- Last BRV
				M	Disc BRV	NA	C-V1

[a] The rationale behind using V1/1BRV in this scenario is based on it being unknown when exactly between V1 and V4 that the first seizure event occurred. V1/1BRV is more conservative and hence will be used, however a sensitivity analysis may be performed if there are a lot of patients with missing data.

Note: M=patient is missing seizure data at this visit but attended the visit, - = patient missed entire visit, NA=Visit is not applicable/not required to be considered in this scenario, V=Visit, C=Censor, E=Event, 1BRV= Date of first dose of BRV, Last BRV= date of last dose of BRV.

Note: V1/1BRV implies the date of the first dose of BRV should be used if it is later than V1 to avoid negative time to events and under-reporting of potential seizure events. For patients with no evidence of seizures on the study, negative censoring times are acceptable as it is equivalent to censoring the patient on Day 1.

The time to first seizure from the date of first dose of BRV will be analyzed using Kaplan-Meier methods, from which the median time to first seizure (and 95% CI) will be calculated, along with 25% and 75% quartiles (and 95% CI for the quartiles). In addition, the cumulative number of events, number at risk, and survival estimate at monthly intervals will be provided. The Kaplan-Meier plot and raw statistical procedure output will be produced for the Kaplan-Meier analysis. This will be performed on the FAS and the modified FAS.

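### Table 8-1 can report a patient as seizure free since first BRV at Month 6 or 12 although seizure data were missing at an earlier attended visit

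*SAP*

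**What the plan says.** SAP section 8.2.2.2, Table 8-1, derives seizure freedom at Months 3, 6 and 12. The rows apply in order: "patients are assigned to the first category they fall into". The parts that matter here are:

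- **Row 1 (No):** "Patient had a seizure on or after 1st BRV dose and on or before the visit date". The variable is therefore cumulative from first dose.
- **Row 3 (Missing):** "Patient had missing seizure data at the visit (or missed the visit) but had not discontinued BRV", with a matching condition on study termination. Only the visit being classified is tested.
- **Row 4 (Yes):** "Patient met none of the above classifications and patient has the visit present". Nothing is required of earlier visits.
- **Footnote:** "For Month 12 assessments, seizure freedom will be analyzed for completers only".

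SAP section 8.2.2.1 states that the count reported at a visit runs from the last visit. SAP section 4.2.1 lets the next visit's diary review cover a missed visit, provided the diaries are available then.

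For time to first seizure, SAP section 8.2.3 says of patients with no evidence of seizures who attended a visit without seizure data that "they will be censored at the date of the last visit prior to the visit with the missing seizure information". Table 8-2 gives this case its own code ("M=patient is missing seizure data at this visit but attended the visit"), separate from the dash for a visit that was not attended.

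**The concern.** If Visit 2 was attended but no seizure data were recorded, the time from Visit 1 to Visit 2 is unobserved, and the Visit 3 count does not reach back over it. A zero at Visit 3 then takes the patient past row 3 and into row 4. The patient is Missing at Month 3 and seizure free since first dose at Month 6. In effect, absent data are read as zero seizures, although SAP section 4.2 says that missing data are not imputed apart from listed exceptions, and this is not among them.

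Seizure freedom at 6 and 12 months is a named secondary variable and serves the study's only secondary objective, seizure control. It is also tabulated by subgroup. The by-patient listing in section 8.2.2.3 shows time to first seizure beside seizure freedom, so one patient can appear there as censored at Visit 1 and as seizure free at 12 months.

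**Working it through.** **1. Logic check.** Inputs are the row order and conditions of Table 8-1, the count interval (section 8.2.2.1) and the missed-visit rule (section 4.2.1). Code each of Visits 2, 3 and 4 as 0 (no seizures), M (attended, seizure data missing) or - (not attended). That gives 3 × 3 × 3 = 27 patterns for an on-treatment completer who is not caught by row 0. Assume that diaries cover missed visits. 'Yes' with an unobserved interval then occurs in 3 patterns at Month 6 (M/0/0, M/0/M, M/0/-) and 5 at Month 12 (M/0/0, 0/M/0, M/M/0, M/-/0, -/M/0).

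The patterns that Table 8-2 also lists are:

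| V2/V3/V4 | Table 8-1, Month 6 | Table 8-1, Month 12 | Table 8-2 |
|---|---|---|---|
| M/0/0 | Yes | Yes | censored at V1 |
| M/0/M | Yes | Missing | censored at V1 |
| M/M/0 | Missing | Yes | censored at V1 |
| 0/M/0 | Missing | Yes | censored at V2 |

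**2. Size.** The plan has no figure to reproduce: it gives neither a missing-data rate nor an expected seizure-free rate. Everything in this step is assumed.

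- Share m of patients with M at Visit 2, unrelated to seizure rate: 10%.
- Baseline rate per 28 days: gamma with mean μ = 3 or 6 and shape k = 0.3 or 1. Counts are Poisson.
- At least one Baseline seizure in three 28-day periods. On-BRV rate 0.6 of Baseline.
- Visits at days 90, 180 and 360. No withdrawals.

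With L(s) = (1 + sμ/k)^(−k), the probability of no seizure over d days on BRV is

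P(d) = [L(0.6d/28) − L(0.6d/28 + 3)] / [1 − L(3)].

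Let S be the true seizure-free rate to the visit and c the probability of no seizure from Visit 2 to that visit. The current rule reports (1 − m)S + mc, so the bias is m(c − S). At Month 6, S = P(180) and c = P(90). At Month 12, S = P(360) and c = P(270).

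Worked case, μ = 3 and k = 0.3:
- S = (0.3317 − 0.2801)/(1 − 0.3569) = 8.0%
- c = (0.4054 − 0.3087)/(1 − 0.3569) = 15.0%
- bias = 0.10 × (15.0 − 8.0) = +0.70 points

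| μ, k | Month 6 S | Month 6 c | Bias | Month 12 S | Month 12 c | Bias |
|---|---|---|---|---|---|---|
| 3, 0.3 | 8.0% | 15.0% | +0.70 | 3.9% | 5.3% | +0.14 |
| 3, 1 | 3.7% | 9.3% | +0.56 | 1.3% | 2.0% | +0.07 |
| 6, 0.3 | 6.0% | 11.3% | +0.53 | 2.9% | 4.0% | +0.11 |
| 6, 1 | 1.9% | 4.9% | +0.31 | 0.6% | 1.0% | +0.04 |

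Among patients with M at Visit 2 and zero at Visit 3, the share wrongly called seizure free at Month 6 is 1 − S/c, about 46% to 62%. The bias is proportional to m: 5% missing halves it and 20% doubles it. It also depends on c − S. With S = 10% and c = 25%, for example, 10% missing gives 0.9 × 10 + 0.1 × 25 = 11.5%, a bias of +1.5 points.

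**3. What reclassification alone would do.** SAP section 3.1 generally keeps patients with missing data in the denominator. If all M-at-Visit-2 patients become Missing, the rate on N is (1 − m)S, a shift of −mS. In the four cases this is −0.2 to −0.8 points at Month 6 and about −0.1 to −0.4 at Month 12. At Month 12 that is further from the truth than the current rule in every case. Among patients with known status, the rate returns to S.

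**The case against.** Several points on the other side have weight.

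- **Row 0.** It sends patients with a seizure before the first BRV dose to Missing. Read literally, it removes most patients, including everyone in the size calculation, before row 4. The calculation therefore holds only if row 0 means something narrower, such as seizures between Visit 1 and first dose. The classification error for those who do reach row 4 is unaffected.
- **Diary review.** Protocol section 11 has the physician review the diary and interview the patient at each visit, and row 1 gives 'No' for any known first-seizure date. This should make gaps rarer. It does not help where nothing was recorded.
- **Missed visits.** A reader might infer that every 'Yes' after a missed visit is also wrong. Section 4.2.1 does not support that: where diaries are available at the next visit, the interval is observed.
- **Different variables.** It is tempting to say that Tables 8-1 and 8-2 contradict each other outright. They define different variables, section 8.2.3 calls its own approach very conservative, and their results would differ anyway because the first method counts discontinuations as not seizure free while Table 8-2 censors them. What stands is narrower: the same gap counts as unobserved in one table and as seizure free in the other, with no reason given.
- **Small effect.** At N = 385 and a true rate of 4% to 6.5%, the 95% half-width, 1.96 × √(p(1 − p)/385), is 2.0 to 2.5 points, well above the modelled bias. The analysis is also descriptive. Both are fair, but this error has a fixed direction and costs little to remove.

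The completers-only footnote and the two discontinuation methods do not answer the point. A completer can lack Visit 2 or Visit 3 seizure data, and both methods give 'Yes' in row 4.

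**Conclusion.** The point holds as a derivation flaw of modest size. For patients who reach row 4, Table 8-1 can certify seizure freedom over an interval with no data, the resulting bias can only be upward, and the treatment is inconsistent with Table 8-2. That much follows from the SAP text alone.

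The size does not. With the assumed seizure rates and 10% missing at Visit 2, it is about +0.3 to +0.7 points at Month 6, on a true rate of about 2% to 8%, and about +0.1 point at Month 12. A reader might infer that the reported seizure-free rates, especially at Month 12, are seriously inflated. The documents do not support that: they give no missing-data rate, and the modelled Month 12 effect is very small.

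**What to change.** Amend row 3 of Table 8-1 so that, unless row 1 or row 2 already applies, the result is Missing when seizure data are absent for any interval between first BRV and the visit. The row should name both ways this happens: an earlier attended visit without seizure data, and a missed visit not covered by diary data at the next attended visit. Row 4 then gives 'Yes' only with complete coverage, and missed visits that the diary does cover stay 'Yes'.

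Because of the section 3.1 denominator, also report seizure freedom among patients with known status, with the number Missing. Otherwise the correction would replace an upward bias with a downward one.

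The cost is one SAP condition, its programming and one extra percentage per table. A few 'Yes' become Missing. The documents do not show whether the CRF records diary coverage after a missed visit. If it does not, that second condition needs case review before database lock, for which the data evaluation meeting is the natural place.

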### 8.2.2.3 Analysis of seizure frequency related variables

The following tables will be produced on the FAS and all tables except the by subgroup tables will be repeated on the modified FAS:

- Descriptive statistics of the POS frequency at Visit 1 (Baseline), Visit 2 (Month 3), Visit 3 (Month 6), Visit 4 (Month 12), and Visit 4 (Month 12/Withdrawal)
- Descriptive statistics of the absolute reduction in POS frequency (seizures per 28 days) from Visit 1 (Baseline) to Visit 2 (Month 3), Visit 3 (Month 6), Visit 4 (Month 12), and Visit 4 (Month 12/Withdrawal)

- Descriptive statistics of the absolute reduction in POS frequency (seizures per 28 days) by subgroups described in [Section 4.8](#), from Visit 1 (Baseline) to Visit 2 (Month 3), Visit 3 (Month 6), Visit 4 (Month 12), and Visit 4 (Month 12/Withdrawal).
- Descriptive statistics of the percent reduction in POS frequency (seizures per 28 days) from Visit 1 (Baseline) to Visit 2 (Month 3), Visit 3 (Month 6), Visit 4 (Month 12), and Visit 4 (Month 12/Withdrawal)
- Number and percentage of responders ( $\geq 50\%$  reduction) at Visit 2 (Month 3), Visit 3 (Month 6), Visit 4 (Month 12), and Visit 4 (Month 12/Withdrawal)
- A sensitivity analysis of the responder analysis will be performed on two subsets of the FAS and modified FAS as defined in [Section 4.6](#) (patients who completed the study and patients who discontinued the study due to lack of efficacy).
- Number and percentage with seizure freedom (using the 2 methods described in [Table 8–1](#)) at Visit 2 (Month 3), Visit 3 (Month 6), and Visit 4 (Month 12)
- A sensitivity analysis of the seizure freedom analysis will be performed on two subsets of the FAS and modified FAS as defined in [Section 4.6](#) (patients who completed the study and patients who discontinued the study due to lack of efficacy).
- Number and percentage with seizure freedom (using discontinuations counted as seizure freedom = no) by subgroups described in [Section 4.8](#), at Visit 2 (Month 3), Visit 3 (Month 6), and Visit 4 (Month 12)

The following by-patient listings of seizure data will be produced on the All Subjects Documented set:

- Seizure Frequency by Type (including by visit data of number of All, POS, and POS with secondary generalization seizures (IC) at Baseline, since the last visit and adjusted for 28-day frequency. In addition, the number of days since last visit, number of days POS occurred since last visit, and the 28-day POS frequency absolute and percentage reduction from Baseline will be presented).
- Time to first seizure (as described in [Section 8.2.3](#)) and seizure freedom, including the date of first and last BRV administration, the date of study termination, the date of first seizure in the study, the time to first seizure, the visit window target dates, and seizure freedom at 3, 6, and 12 months (using the 2 methods described in [Table 8–1](#)).

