### **2.4 Determination of sample size**

Initially, a sample size of 430 patients was chosen for this study in order to obtain 385 patients in the Full Analysis Set (FAS), which allows for approximately 10% of patients to not be included.

When the sample size is 385, a 2-sided 95% confidence interval (CI) for a single proportion using the large sample normal approximation will extend 0.05 from the observed proportion for an expected proportion of 0.50. As an example, given an observed retention rate of 50%, a sample size of 385 patients would give a 2-sided 95% CI of 45% to 55% based on the large sample normal approximation to the binomial distribution.

However, since the first 100 patients were all enrolled at sites in Germany in early 2016 and the enrollment in that country was closed, it was believed that ongoing enrollment in other countries would be following different best practices in BRV usage, which could lead to wide variation in this NIS. For this reason, 100 additional patients are planned to be enrolled to obtain 385 patients in the FAS at non-German sites.

It is, therefore, planned to have 530 patients, and withdrawals will not be replaced.

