### 3.2.2 Visit 4, Month 12/Withdrawal Visit

Patients with early study termination (ie, those who complete the Study Termination [Dropout] CRF page), will have their Visit 4 (Month 12/Withdrawal) visits prior to the preferred visit window for Month 12 of greater than or equal to 330 days after date of first BRV administration. Patients completing the study (ie, those who complete the Study Termination NIS [Completed Subject] CRF form), will have their Visit 4 (Month 12/Withdrawal) visits within the preferred visit window for Month 12 of greater than or equal to 330 days after date of first BRV administration. Therefore, Visit 4 will be analyzed as follows depending on the objective and variable being analyzed:

- Visit 4 (Month 12): Including only patients who are study completers with a Visit 4 within the preferred visit window for Month 12 of greater than or equal to 330 days after the date of first BRV administration.
- Visit 4 (Month 12/Withdrawal): Including all data recorded at Visit 4 (ie, completers or patients who withdraw early)

In addition, Visit 4 (Month 12/Withdrawal) visits that correspond to scheduled visits will be included in the counts for the scheduled visits to which they correspond. To be classed as corresponding to the scheduled visit, the withdrawal visit must fall into the windows provided below and the patient have no scheduled visit already available. Only the variables below will have the mapping of withdrawal visits applied.

Variables	Visit 2, Month 3	Visit 3, Month 6
Disposition (Patients attending each visit)	30-135	136-329
Seizure Frequency	30-135	136-329
QOLIE	30-135	136-329
CGIC/PGIC	30-135	136-329
EpiTrack	No mapping as no scheduled visit	150-210

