#### **4.6 Use of subsets of subjects**

All effectiveness analysis will be performed on the FAS and the modified FAS to estimate the effectiveness for patients using BRV per the approved SmPC.

In addition, the responder analysis and the seizure freedom analysis will be repeated on the FAS and modified FAS for:

- patients who completed the study
- patients who discontinued the study due to a lack of efficacy

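### The completer and lack-of-efficacy responder subsets do not test how dropouts are handled, and no response rule counts stopping BRV as non-response

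*SAP*

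**What the plan says.** SAP 8.2.2.3 plans the number and percentage of responders at Month 3, Month 6, Month 12 and Month 12/Withdrawal. It then adds: "A sensitivity analysis of the responder analysis will be performed on two subsets of the FAS and modified FAS". SAP 4.6 names the subsets: patients who completed the study, and "patients who discontinued the study due to a lack of efficacy".

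SAP 3.2.2 fixes who is counted at the last visit: "Visit 4 (Month 12): Including only patients who are study completers with a Visit 4 within the preferred visit window", that is, at 330 days or later. A separate summary, Visit 4 (Month 12/Withdrawal), takes everything recorded at Visit 4, including early withdrawals. For seizure frequency, a withdrawal visit on Days 30 to 135 is mapped to Month 3, and one on Days 136 to 329 to Month 6, if the patient has no scheduled visit there.

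Under SAP 8.2.2.2, response is Yes for a reduction of at least 50% and No otherwise; patients with no POS at Baseline are excluded. SAP 8.2.2.1 calculates a frequency only at attended visits with seizure data and leaves missing Visit 4 rates missing. SAP 4.2 imputes nothing beyond listed exceptions, and response is not among them.

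Seizure freedom is handled differently. Row 2 of Table 8-1 counts discontinuation before the visit's target day as not seizure free under the first method. Footnote [a] removes this at Month 12: "Therefore assign missing to all patients who withdraw for the Month 12 analyses".

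**The concern.** A sensitivity analysis should vary an assumption that could change the answer. Here that assumption is the treatment of patients who leave: are they failures, are they missing, or are they scored on their last visit? Restricting the table to patients who stayed, or to those declared failures, leaves that assumption unchanged and alters only who is looked at.

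The secondary objective is seizure control with BRV, and the study is descriptive, so these percentages are the result. If Month 12 response is reported among completers and a completer repeat stands beside it under the name of a sensitivity analysis, readers may credit the figure with a robustness that was not examined. Meanwhile a patient who stopped BRV can appear as a responder, as missing, or inside an unexplained denominator, depending on the visit and on an unstated programming choice.

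**Working it through.** **1. The plan's own figure.** SAP 2.4 gives no planning value for response; its only figure is for retention. The 95% CI "will extend 0.05 from the observed proportion for an expected proportion of 0.50". Check: n = 1.96² × 0.5 × 0.5 / 0.05² = 384.2, so 385, with half-width 1.96 × √(0.25/385) = 0.0499. SAP 2.4 also says "a sample size of 430 patients was chosen for this study in order to obtain 385 patients". With its allowance of about one patient in ten falling outside the FAS, 385/0.90 = 428, close to 430. The figures reproduce and are unaffected by this point. They supply the FAS size and the 50% example retention used in step 5.

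**2. Who has response data at each timepoint** (SAP 3.2.2 with 4.6).

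| Timepoint | Main FAS table | Completer subset | Lack-of-efficacy subset |
|---|---|---|---|
| Month 3 | attenders, plus mapped withdrawals Days 30–135 | attenders who later completed | attenders who later left for this reason, plus mapped withdrawals |
| Month 6 | attenders, plus mapped withdrawals Days 136–329 | as above | as above |
| Month 12 | completers at ≥330 days | the same patients and the same responders | nobody |
| Month 12/Withdrawal | all Visit 4 data | completers' Visit 4 data | withdrawal-visit data |

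The duplicate and the empty table are therefore confined to Visit 4 (Month 12). The other three timepoints have data in both subsets, selected on outcome.

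**3. How a stopper is scored.** Take a patient who stops BRV and has the withdrawal visit on Day 40, with a reduction of at least 50% since Visit 1 and no scheduled Month 3 visit. Day 40 lies in the 30–135 window, so the patient is a Month 3 responder. Under the 90-day rule in SAP 8.2.1 the same patient is not retained at 3 months. A withdrawal visit after Day 135 but before Day 180 has the same effect at Month 6. At Month 12 the patient has no value.

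**4. The denominator.** SAP 3.1 says that, in general, a missing row is added and percentages use the analysis-set N. That would put stoppers in the denominator. SAP 8.2.2.3 names no denominator for the responder table, and SAP 8.2.2.2 removes zero-Baseline patients from the analysis, so analysis-set N cannot apply unmodified. Read literally, the words that score everything else as No would make stoppers non-responders; SAP 4.2 and 8.2.2.1 point to missing instead.

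**5. Size (illustration).** The documents give no response rate. Assumed: FAS 385; retention 50%, so 192 completers and 193 stoppers; completer response 50%, so 96 responders. Completers are equated with retained patients, and zero-Baseline patients and missed visits are ignored.

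- Patients with Month 12 data: 96/192 = 50.0%, the same as the completer subset.
- FAS denominator, or stoppers counted as non-responders: 96/385 = 24.9%.
- Month 12/Withdrawal, with 0%, 20% or 40% of stoppers responding at their withdrawal visit: (96 + 0)/385 = 24.9%, (96 + 38.6)/385 = 35.0%, (96 + 77.2)/385 = 45.0%.

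In general, the figure with stoppers as failures is retention × completer response. With 50% completer response, retention of 60% or 70% gives 0.6 × 0.5 = 30% or 0.7 × 0.5 = 35%. Over assumed ranges of 50–80% retention and 30–60% completer response it runs from 0.5 × 0.3 = 15% to 0.8 × 0.6 = 48%. The gap to the completer figure is completer response × (1 − retention): from 0.3 × 0.2 = 6 points to 0.6 × 0.5 = 30 points.

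**The case against.** Three arguments have weight.

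First, if the general rule in SAP 3.1 governs, the FAS table divides the Month 12 responders by FAS N and the completer table divides the same responders by completers. In the illustration these are 24.9% and 50.0%, so the two planned tables together would display the gap. This stands. A reader might infer that the planned tables must agree, or that they would show none of the gap. The documents do not support either inference: identity is certain for evaluable patients and responder counts, but for the percentage only with a patients-with-data denominator. What remains is that the rule is hedged, and that a missing row pools stoppers with patients still on BRV who lack diary data, groups that Table 8-1 separates.

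Second, early leavers are not ignored. Month 12/Withdrawal includes them, mapping brings them into Months 3 and 6, and comparing the FAS with completers there shows how much they shift the result. This also stands. However, that comparison scores leavers on their withdrawal visit, where they can be responders; it never asks what happens if stopping counts as failure.

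Third, the study is descriptive and exploratory, Protocol 12.2 analyzes withdrawals up to their final visit, and discontinuation is itself the primary variable. A reader could multiply retention by completer response. That works approximately at Month 12. At Months 3 and 6 it does not, because mapped withdrawals already sit among the responders, and the retention denominator includes zero-Baseline patients.

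**Conclusion.** The point holds in a limited form. The two subsets are outcome-selected at every timepoint and do not test the handling of dropouts. At Visit 4 (Month 12) one adds no patient or responder to the main table and the other is empty. No response rule explicitly counts stopping BRV as non-response, and the denominator that would decide this implicitly is unclear.

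Under the stated assumptions the choice moves Month 12 response from 50% to about 25%. Only the 50% retention comes from the SAP, and there it is an example for precision; the response rates and the other retention values are assumptions.

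One further inference should be avoided: that seizure freedom under the first method is No by definition in the lack-of-efficacy subset. Table 8-1 assigns patients to the first row that fits. Row 0, a seizure before the first BRV dose, gives Missing before row 2 is reached, and footnote [a] sets withdrawals to missing at Month 12.

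The change is worth making before the tables are final. The primary retention analysis and the sample size are not affected.

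**What to change.** In SAP 8.2.2.3, state the responder denominator at each visit, and say whether the general rule in SAP 3.1 applies once zero-Baseline patients are excluded.

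Add one responder analysis in FAS patients with Baseline POS above zero, at Months 3, 6 and 12. A patient who discontinued BRV or the study before Day 90, 180 or 330 respectively is a non-responder. This is the row 2 rule of Table 8-1 with the SAP's own target days, applied at Month 12 as well and therefore without the footnote [a] exception. Show patients still on BRV with no seizure data separately as missing.

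Keep the completer and lack-of-efficacy tables, but call them descriptive in SAP 8.2.2.3 rather than sensitivity analyses.

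The cost is a few lines of SAP text and one more table from dates already derived. The downside is a less favourable responder percentage printed beside the completer figure.
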